## POSSIBLE ISSUES

**Age.** While it is true that the age for our participants may be somewhat younger (50 or older) than most studies of the elderly, we believe that this range is common in individuals with HIV infection and will include persons with age-related cognitive changes. The mean age in a study showing that frailty was associated with multimorbidity for example, was 46 years.

**Game-based cognitive training includes many elements – how to determine what is the active ingredient?** It is true that action games require a wide range of cognitive skills across a variety of contexts with

repetition in multiple situations. Bavelier et al. argue that it is precisely this aspect of game playing that promotes transfer of training from the game to other activities, unlike other cognitive training programs.

**Single blind.** Especially given the importance of rigor and reproducibility in NIH-sponsored research, the use of a single blind design may raise concerns. This concern is balanced with the need to use devices FDA-approved for use with humans and the previous success of the single blind strategy in other trials as well as the pilot study.

**Depression vs cognition.** Results of the pilot study as well as other studies show that tDCS may improve both cognition and mood. Our pilot study reflects changes in both. Including change in depression in analyses reduced the effect size of treatment on self-report of cognitive difficulties, but increased the effect size for cognitive measures. We thus will explore the extent to which change in mood affects cognition by examining it as a covariate and, if warranted, in a mediation analysis.

**Multiple covariates with small sample.** In analyses for the preliminary study, it was judged important to include multiple potential covariates (age, gender, race, immune status) to evaluate treatment effects, even with a small but heterogeneous sample. Given larger samples in most studies this may seem inappropriate, but we note that in his first presentation of analysis of covariance (ANCOVA) in 1934, Fisher used four measurements on four entities (tea producing plots in Ceylon) to demonstrate the technique's utility.

**Future studies** will examine the impact of ongoing training over a longer period and the usefulness of booster sessions. If this study suggests an impact on functional status, a future study might evaluate the impact of the intervention on biological markers of illness and actual performance of the activities of daily living.

DATA ANALYSIS PLAN

Computer Training and Transcranial Direct Current Stimulation for Cognition in HIV

Identifier: NCT03440840

National Institute on Aging grant: R21AG056256

Date: 12/2/2020

DATA ANALYSIS PLAN

A mixed models approach to repeated measures analysis will be used to test core study hypotheses. Potential confounders found important in the pilot study will be examined via correlations and included in analyses as indicated. Based on our pilot study, these variables are likely to include age, gender, race, education, mood, and immune status markers.

Power analysis. Power analyses were completed using the mixed models simulation routine in PASS 11¹²⁵ and with estimates of effect size based on results of our pilot study and 1,000 simulation runs. A sample size of 30 per group provides a power of 0.88 (95th %ile confidence interval 0.87 – 0.91) to detect the interaction of group membership over assessments for cognitive and self-report measures.

Data preparation and preliminary analyses. Statistical tests for skew and kurtosis will be obtained, as well as visual inspections of the empirical distributions. Any significant deviations from normality will be addressed through transformations of the data and if transformations are not possible, non-parametric approaches to the planned analyses will be employed. Reliability estimates of the internal consistency of measures (Cronbach's alpha) will also be examined. Statistical tests of between-group baseline differences on key variables will also be conducted to ensure effectiveness of the randomization procedure.

Missing data. Although we will make every effort to minimize loss to follow-up, we recognize some attrition is likely over time. Multiple imputation (MI) will be employed to address missing data. MI creates plausible values for missing data while preserving the underlying data distribution's characteristics.¹²⁶ MI is based on the assumption of missing-at-random (MAR), which is plausible in a closely-controlled study such as this. Whereas mixed models are robust to MAR data without the use of MI, MI has also been shown to improve performance when data is missing not at random and an inclusive strategy, as we plan to use, is followed.¹²⁷

Test of hypotheses. We will evaluate hypothesis 1 in SPSS, and evaluate hypothesis 2 treatment effects in intent to treat analyses in mixed models evaluated in the MPlus statistical software.¹²⁸

Hypothesis 1: *A game-based cognitive training intervention combined with tDCS will be acceptable to older persons with HIV infection.* We will test this hypothesis based on participant ratings of the intervention on the Usability scale of our questionnaire based on the Technology Acceptance Model. Using a single sample *t* test, we will assess whether ratings are significantly greater than the midpoint of the scale.

Hypothesis 2: *Action game based cognitive training will be superior to strategy game based training, while action game training with tDCS will be superior to training alone (control + sham < training + sham < training + tDCS) on objective measures of reaction time, attention, and psychomotor speed.* Outcome measures will be CalCap (reaction time), Digit and Spatial Span (attention) and Grooved Pegboard and Trail Making Test Part B (psychomotor speed).

Sex as a biological variable. As discussed above, we will work to ensure that substantial numbers of women participate in this study. Given data suggesting that HIV infection may differentially affect cognition in women compared to men,^{72,75} we will evaluate sex as a covariate in analyses and explore the possibility of sex differences in cognitive function and response to training.

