**Transcranial direct current simulation (tDCS)** has emerged as a safe and inexpensive strategy to enhance the effects of cognitive training. Studies show substantial increases in amount and rate of learning in healthy young as well as older persons, and patient groups that have included individuals with neurological disorders such as primary progressive aphasia or Parkinson's disease. tDCS may also have positive effects on depression, and was acceptable to participants as a treatment for depression in HIV. **tDCS is thus a promising technique to enhance cognitive training in older persons with HIV.**

**While tDCS is an emerging treatment, it is the subject of serious investigation.** Noninvasive brain stimulation technologies, including tDCS, were described as promising at a workshop at the Institute of Medicine in 2015, and the NIMH Division of Translational Research will have held a workshop on tDCS by the time this application is reviewed (scheduled for 9/29-30/16).

To study tDCS and cognitive training in HIV, we completed a **pilot study** of computer game based cognitive training with and without tDCS in older persons (average age 51 years) with HIV. **Results suggest a positive effect of tDCS on cognition and mood and demonstrate the potential feasibility and acceptability of the intervention.** Given the preliminary nature of the proposed study, we are seeking support under the R21 exploratory/developmental mechanism ("high risk – high reward") in response to the PAR 15-282, "Multidisciplinary Studies of HIV and Aging" to further explore the usefulness of cognitive training and tDCS in persons with HIV.

**We will complete a randomized, single-blind treatment with blinded outcome assessments study of game-based cognitive training with and without tDCS, with an attention control group, recruiting 125 persons to ensure a total sample of 90 individuals 50 years of age and older with HIV-related mild neurocognitive disorder, to evaluate the following:**

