## AIMS AND HYPOTHESES

**AIM 1) Further explore the acceptability and feasibility of game-based cognitive training with and without tDCS in older persons with HIV infection** by completing a trial that includes a control as well as groups receiving cognitive training with and without tDCS.

***Hypothesis 1:** A game-based cognitive training intervention combined with tDCS will be acceptable to older persons with HIV infection.*

**AIM 2) Evaluate the effects of game-based cognitive training with and without tDCS on cognition in older persons with HIV.**

***Hypothesis 2:** Action game based cognitive training will be superior to attention control, while action game training with tDCS will be superior to cognitive training alone (**control + sham < training + sham < training + tDCS**) on measures of reaction time, attention, and psychomotor speed.*

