## B. INNOVATION

[figure not shown]
The proposed study is innovative in its use of a computer-based game for cognitive training in HIV and its combination of cognitive training with tDCS. No readily identifiable study has examined gaming or tDCS to improve cognition in persons with HIV infection; this study will allow an evaluation of an action game requiring quick reactions, sustained attention and psychomotor speed, and the combination of an action game with tDCS as well as provide a contrast with computer-based learning (attention control). Other researchers have examined each of these strategies in healthy older adults and in some patient groups, but this study would be innovative in allowing an assessment of the effects of cognitive training with and without tDCS in HAND.

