## PLANNED STUDY

**Overview.** This will be a randomized, single-blind trial with blinded outcome assessments evaluating the effects of computer game based cognitive training with or without tDCS compared to an attention control, watching educational videos on a computer (Figure 4). We will enroll 120 participants to obtain a final n of 90

(allowing for attrition) who will be randomly assigned in equal numbers to (1) attention control (educational videos + sham tDCS), (2) cognitive training with an action (car racing) game + sham tDCS, or (3) cognitive training with an action game + active tDCS. The study will thus implement the training protocol from the pilot study (which participants found enjoyable and subjectively helpful) but will now include an attention control group to help evaluate nonspecific effects of

computer use. This study will also expand the assessment battery to include measures of functional status, motor function, frailty, driving, and medication adherence. We will ask participants to return for a follow-up one month after the final visit to determine if training effects are maintained, laying the groundwork for a larger study that could explore strategies to maintain treatment effects if they are obtained.

**Inclusion.** Participants will be treated for HIV infection, on a stable regimen of antiretroviral medications for at least one month, aged 50 years or older, and meet Frascati criteria for mild neurocognitive disorder based on report of cognitive difficulties and cognitive deficits in two domains as determined by neuropsychological testing. **Exclusion.** Participants will be excluded if they have conditions that might affect their safety when receiving tDCS (e.g., seizure disorder), or on medications that can affect tDCS (psychotropic medications can affect how tDCS works) or are severely cognitive impaired.

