In light of the importance of evaluating the practical significance of training effects as well as their impact on laboratory cognitive measures, the battery includes a measure of health-related quality of life (SF-36) and a self-report measure of instrumental activities of daily living. We will ask participants about their adherence to medication and other treatments using a previously validated strategy. Given the potential relation of psychomotor speed to driving, we also include a self-report measure of driving habits sensitive to mild cognitive impairment.

**Training.** All participants will complete six 20-minute training sessions in our computer lab. Sponge electrodes (25cm^2) will be placed over the left dorsolateral prefrontal cortex (anode) and the right supraorbital area (cathode). In the **active tDCS** condition, participants will receive 1.5 mA stimulation for 20 minutes while they will play the car racing game. In the two **sham conditions**, the tDCS will be turned on and current allowed to ramp up over 30 s to 1.5 mA after which the device will be switched off. The racing + sham tDCS will then play the car racing game for 20 minutes, and the attention control group will watch a 20-minute educational video with sham tDCS and respond briefly to questions about its content as used in other studies and our own unpublished study. Immediately after each session, participants will respond to rating questions about cognitive function, mood, and discomfort.

**Post-test and Follow-up.** After completing six training sessions, participants will complete the same assessment battery as at baseline, and again one month later (see Appendix and Figure 4).

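### Does SAP Hypothesis 2 set the action game against a strategy game that no arm plays?

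*SAP*

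**What the plan says.** The SAP, under Hypothesis 2, states that "Action game based cognitive training will be superior to strategy game based training". The same sentence adds that the action game with tDCS will beat training alone, and sums up the prediction as "control + sham < training + sham < training + tDCS". It then lists the outcome measures: CalCap, Digit and Spatial Span, Grooved Pegboard and Trail Making Test Part B.

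The protocol's version, under Aims and Hypotheses, reads "Action game based cognitive training will be superior to attention control" and carries the same three-step ordering. Other sections of the protocol agree with it:

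- Rationale for Study describes "game-based cognitive training with and without tDCS, with an attention control group".
- Innovation says the study will "provide a contrast with computer-based learning (attention control)".
- Planned Study, Overview, has training "compared to an attention control, watching educational videos on a computer" and lists the first arm as "attention control (educational videos + sham tDCS)".
- Procedures, Training, says that "the attention control group will watch a 20-minute educational video with sham tDCS".

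The other two arms are the car racing game with sham tDCS and the action game with active tDCS.

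**The concern.** Read alone, the SAP's opening clause names a comparator that nobody in the trial receives, and it does so in the first contrast of the only efficacy hypothesis. Taken literally, that contrast could not be tested with the arms described.

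The two possible comparators also answer different questions. Superiority over an educational video would support a benefit of action gaming over passive computer use. Superiority over a strategy game would support a benefit specific to the type of game. The SAP does not describe the control anywhere else, so a reader with only that document could attach the wrong meaning to a positive result.

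**Working it through.** This is mainly a comparison of texts. The one nearby figure, the power, is checked for any dependence on the comparator's name.

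**1. The two versions of Hypothesis 2.**

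| Element | Protocol | SAP |
|---|---|---|
| Comparator named in the first clause | attention control | strategy game |
| Ordering in the parenthesis | control + sham lowest, then training + sham, then training + tDCS | the same |
| Outcome domains | reaction time, attention, psychomotor speed | the same |

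The substantive difference is the comparator in the first clause.

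**2. The SAP ordering against the randomised arms.**

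| Term in the ordering | Arm in Planned Study, Overview |
|---|---|
| control + sham | educational videos, sham tDCS |
| training + sham | car racing game, sham tDCS |
| training + tDCS | action game, active tDCS |

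Three terms match three arms with none left over. The ordering calls the lowest group a control and keeps the word training for the other two. A strategy game described as training does not fit that scheme; the video control does.

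**3. How firmly the protocol identifies its control.** Uses of the term attention control in the protocol body: Rationale 1, Aims and Hypotheses 1, Innovation 1, Planned Study Overview 3, Procedures 1. The total is 1 + 1 + 1 + 3 + 1 = 7, in five sections. Arms, procedures or hypotheses in the protocol that mention a strategy game: 0. The phrase appears elsewhere only in the title of a cited background study in the reference list.

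**4. What the analysis uses.** The SAP specifies mixed models for repeated measures, by intent to treat, with power stated for the interaction of group with assessment. The grouping variable is the randomised arm. Renaming one arm changes no data, contrast or estimate.

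**5. Whether the power figure depends on the name.** The stated power is 0.88 with 30 per group, and 3 × 30 = 90 agrees with the protocol's target of 90 completers. The figure cannot be reproduced, because the effect size, correlation, alpha and sidedness used in the simulation are not stated. As context only, assume alpha 0.05 and a simple two-group comparison. The standardised difference giving power 0.88 is then

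- two-sided: (1.960 + 1.175) × √(2/30) = 0.81
- one-sided: (1.645 + 1.175) × √(2/30) = 0.73

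No term in these formulas refers to what the control group does. The SAP takes its effect sizes from the pilot, which compared training with and without tDCS and had neither a video nor a strategy-game control. Correcting the name would therefore leave the power input as it is.

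**6. Where the phrase probably came from.** The SAP cites references 125 to 128. These are listed in the protocol's reference list but not cited in its body, which goes from 124 (Procedures) to 129 (Possible Issues). The two texts therefore appear to be parts of one application, and a leftover phrase is the likeliest explanation. This is an inference, and the conclusion does not rest on it.

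**The case for a change.** The strongest case for acting is that the correction costs one clause, the clause sits in the only efficacy hypothesis, and a public SAP should name its comparator correctly without help from another document. It can be added that the SAP is dated 12/2/2020, whereas the protocol text treats a workshop of 9/29-30/16 as still to come. A change of control activity in between cannot be strictly excluded.

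Part of this stands. The clause is wrong as written against the protocol, it is not an artefact of extraction or redaction, and the risk of misreporting from the SAP alone is not zero.

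It does not amount to a flaw in the plan. The testable comparison is in the same sentence, so even a reader of the SAP alone sees a control group with sham stimulation at the bottom of the ordering. As for a later change, neither document records one, and the SAP keeps the protocol's ordering unaltered. Had the control activity changed, the open question would be what that arm received. The analysis would still compare the same three randomised groups.

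**Conclusion.** The inconsistency is genuine but clerical. It affects one clause in one of two hypotheses. It has no effect on the sample size, the stated power of 0.88, the model, the outcome measures or any estimate. The intended contrast is action game plus sham against educational-video control plus sham. It can be recovered from the ordering in the SAP's own sentence and from five sections of the protocol, and an analyst holding both documents would fit the same model and report the same comparison with or without a correction.

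This rests on two assumptions: that the control group received what the protocol describes, and that results are reported with the arm as the protocol defines it. Both are reasonable on the documents, so no change to the plan is needed.

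### Hypothesis 2 claims two superiority steps on five measures, but the plan has no success rule and no error control, and the only effect it names cannot show the ordering

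*SAP*

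**What the plan says.** - **Claim.** SAP, Hypothesis 2, gives the ordering "control + sham < training + sham < training + tDCS". That is two steps: training over control, and training with tDCS over training alone.
- **Measures.** "Outcome measures will be CalCap (reaction time), Digit and Spatial Span (attention) and Grooved Pegboard and Trail Making Test Part B (psychomotor speed". That is five tests, with none named primary and no composite.
- **Analysis.** "A mixed models approach to repeated measures analysis will be used to test core study hypotheses". The SAP adds that Hypothesis 2 is analysed by intent to treat. It gives no alpha, contrast, time point or multiplicity method.
- **Effect named.** The SAP's power paragraph gives 0.88 power with 30 per group "to detect the interaction of group membership over assessments for cognitive and self-report measures".
- **Timing.** The protocol's Planned Study overview asks participants to "return for a follow-up one month after the final visit to determine if training effects are maintained". This implies that the main comparison is at post-test, but the SAP does not say so.
- **First comparator.** The SAP's sentence begins "Action game based cognitive training will be superior to strategy game based training". The protocol's Hypothesis 2 reads "Action game based cognitive training will be superior to attention control", and its Planned Study overview defines that arm as "attention control (educational videos + sham tDCS".

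Hypothesis 1, by contrast, has a named scale, a named test and a threshold (the scale midpoint).

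**The concern.** Two steps on five measures make ten directed comparisons. With no stated rule, the analyst could declare Hypothesis 2 supported after seeing the data because of one favourable test, one favourable step, a significant interaction, or the full ordering. These rules have very different chances of a false claim.

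The interaction is a particular problem. With three arms it asks only whether the groups change differently. It can be significant because training beats the videos while tDCS adds nothing, and the tDCS step is the more novel half of the hypothesis.

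What is at stake is whether a report that tDCS enhances training, offered as groundwork for a larger study, would rest on a test of that statement.

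**Working it through.** **The plan's own figure.** The 0.88 power cannot be reproduced, because the SAP gives no alpha, effect size, SD or within-person correlation. As a reference only: a simple 30 v 30 comparison at two-sided 5% has 0.88 power when d = (1.960 + 1.175) × √(2/30) = 0.81.

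**Inputs.** From the documents: three equal arms, 30 per arm, five measures, two adjacent steps. Assumed, because the documents are silent: two-sided 5% tests, one time point, equal correlation r between measures of 0.3, 0.5 or 0.7.

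**1. False claims when nothing works.** Let G1, G2 and G3 be the standardised arm means on a measure. The step statistics are z1 = (G2 − G1)/√2 and z2 = (G3 − G2)/√2; they share the middle arm, so their correlation is −0.5. A false claim is z > 1.96, nominally 2.5% per test. Simulation with 400,000 draws gives:

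| Rule for support | r = 0.3 | r = 0.5 | r = 0.7 |
|---|---|---|---|
| Any of five measures, one step | 0.103 | 0.092 | 0.074 |
| Any of ten tests | 0.205 | 0.182 | 0.148 |
| Any of five omnibus tests (nominal 5% each) | 0.211 | 0.186 | 0.153 |
| Both steps on the same measure | at most 0.00003 | at most 0.00003 | at most 0.00003 |
| Any of ten, with Holm | 0.024 | 0.022 | 0.019 |

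Hand check for independent tests: 1 − 0.975⁵ = 11.9% and 1 − 0.975¹⁰ = 22.4%. The simulated values lie below these, as positive correlation between measures should make them.

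**2. The interaction when training works and tDCS adds nothing.** With one post-baseline visit the interaction is a three-group test of change. Arm means are 0, d, d with SD 1, so the noncentrality is 30 × (2/3) × d² = 20d², and the 5% critical value of F(2, 87) is 3.10.

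| Assumed training effect d | 20d² | Chance of significance |
|---|---|---|
| 0.2 | 0.80 | 11% |
| 0.3 | 1.80 | 20% |
| 0.5 | 5.00 | 49% |
| 0.84 | 14.11 | 92% |

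The protocol's Rationale and Significance sections expect training effects to be small, which points to the upper rows.

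**3. Price of error control.** For a 30 v 30 t-test the noncentrality is d × √15. The illustrative d values, 0.75 and 0.84, are the pilot results for Grooved Pegboard and Trail Making B (protocol, Table 1). They come from 11 people and bear only on the tDCS step, because the pilot had no attention control.

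| d | d√15 | Power at 5% | At 2.5% (Holm, first of two) | At 0.5% (Holm, first of ten) |
|---|---|---|---|---|
| 0.75 | 2.905 | 0.815 | 0.726 | 0.500 |
| 0.84 | 3.253 | 0.892 | 0.827 | 0.631 |

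**The case against.** Read literally, Hypothesis 2 is a conjunction: training beats its comparator and tDCS beats training alone. One chance result does not meet that wording. On that reading, for one named measure, the false-claim rate is below 0.01% when nothing works. If training works and tDCS does not, it is at most 2.5%, the chance of one false tDCS result in the predicted direction. This is correct, but the SAP never says that both steps are required, or on which measure.

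The SAP also does not prescribe the interaction as the decision test. It appears only as the effect that was powered, and a mixed model can estimate the directed contrasts. That stands too. The point is that no other effect is named.

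Finally, this is an exploratory R21, so strict alpha control may be out of proportion. That lowers the consequence and makes an exploratory label a full remedy. It does not supply a rule for a hypothesis worded as superiority.

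A reader might infer four stronger things that the documents do not support:

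- **That the trial's error rate is 15-21%, or even 40% (1 − 0.95¹⁰).** The first figure needs an any-one-of-ten rule that nobody has stated. The second also treats the tests as independent and counts results in the wrong direction.
- **That a misleading interaction is near certain (92%).** This needs a training effect of 0.84, which the protocol does not expect.
- **That neither contrast is defined.** The two arms of the tDCS step agree throughout. Only the label of the first comparator conflicts, and the SAP's own ordering calls that arm control.
- **That Digit Span adds more tests because the pilot reported three scores.** The score may be fixed in the assessment appendix, which is not available here.

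**Conclusion.** The gap is real and should be closed before analysis. Hypothesis 2 has no primary measure, no error control and no success rule, and the one effect named does not test the ordering. With no true effects, the chance of a false claim runs from below 0.01% (both steps on one measure) through 7-10% (any measure, one step) to 15-21% (any of ten tests), so it is set by a choice that the plan leaves open. If training works and tDCS does not, a single omnibus test would be significant in roughly 11-49% of trials for training effects of 0.2 to 0.5.

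These sizes rest on assumed two-sided 5% tests, correlations of 0.3 to 0.7, one time point and 30 per arm. The absence of a rule rests on no assumption. The exploratory purpose makes this a point that should be corrected, not one that undermines the trial.

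**What to change.** In the SAP:

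1. Judge Hypothesis 2 on the two adjacent between-arm contrasts of change from baseline to post-test, taken from the planned mixed model and not from the omnibus interaction. Report the one-month visit as maintenance.
2. Choose one rule:
   - require both steps on one named primary measure, each at 5% with no split;
   - claim the steps separately, with Holm over the tests used; or
   - label Hypothesis 2 exploratory, report estimates and intervals for all five measures, and claim no support from single p-values. This fits the R21 purpose best.
3. Correct the first comparator in the SAP's Hypothesis 2, which no arm receives, to agree with the protocol's Hypothesis 2 and Planned Study overview.

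**Cost.** Wording only, with no added participants or visits. Holm lowers single-test power from about 81-89% at 5% to 73-83% at the first step over two contrasts, or 50-63% over ten (d = 0.75 to 0.84). Requiring both steps gives 64-79% if each step has such an effect, but less if training effects are small: the training step alone then has about 12%, 21% and 49% power at d = 0.2, 0.3 and 0.5 (normal approximation). The exploratory label costs no power but gives up a claim of support.
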